#### PRIMARY ANALYSISAA

The unit of analysis will be the city (i.e., composite curable STI prevalence at the city level). This approach is appropriate since the sample size is approximately the same from city to city. The primary analysis of intervention efficacy will be based on the model

$$d_i^O = b_0 + b_1 d_i^B + \varepsilon_i \quad (M1)$$

where  $d_i^O$  is the difference in the primary composite STI endpoint [gonorrhea, chlamydia, vaginal trichomonas, and syphilis seroreactivity (RPR  $\geq 1:8$ , TP•PA confirmed)] between the intervention and control communities (control – intervention) of the  $i$ th pair in the final (2006) outcome survey,  $d_i^B$  is the corresponding difference in the baseline (2002) survey and  $\varepsilon_i$  is a random error. The hypothesis of interest is

$$H_0: b_0 = 0 \quad (\text{no intervention effect}) \quad (H1)$$

---

AA Primary and secondary analysis descriptions taken from “PREVENanalysisPlan\_23.01.07.doc” dated 1/24/07 and updated 3/18/09

Ha:  $b_0 \neq 0$  (intervention effect)

Note that if  $d_i^B$  was not included in the model, this analysis would be equivalent to a paired t-test. The  $d_i^B$  term is included in the model to control for differences in STI prevalence at baseline (which may occur in spite of the matching).

Least squares regression will be used for model fitting. The standardized test statistic  $\hat{b}_0 / se(\hat{b}_0)$  from this analysis has a t-distribution with 8 degrees of freedom. A p-value will be reported for the hypothesis (H1) and a type I error rate ( $\alpha$ ) of 0.05 (two-tailed) will be used to reject/fail to reject the null hypothesis (H1).

The endpoint in the primary analysis will be the composite curable STI endpoint [combined gonorrhea, chlamydia, vaginal trichomoniasis, or syphilis (RPR  $\geq 1:8$ , TP•PA confirmed)] as measured in the GP.

## SECONDARY ANALYSIS

The analysis outlined above was used for the following endpoints:

- Composite curable STI prevalence [gonorrhea, chlamydia, vaginal trichomoniasis, or syphilis (RPR  $\geq 1:8$ , TP•PA confirmed)] in FSW
- Individual STI in GPS
- Individual STI in FSW

## POWER CALCULATIONSBB

In Table 2 we present power calculations for testing for a 30-50% reduction in the primary STD outcomes between the treatment and control communities based on the random

---

BB Power calculations taken from “PREVEN trial summary.doc” dated 3/7/06 and presented for DSMB review in April 2006.

population survey of 600 men and women per city. The FSW population is considered separately. These calculations make use of the standard sample size/power formula for matched community randomized trials, as shown below.

$$n = 2 + \frac{(Z_{1-\alpha} + Z_{1-\beta})^2 \left[ p_1(1-p_1)/f + p_2(1-p_2)/f + k^2(p_1^2 + p_2^2) \right]}{(p_1 - p_2)^2}$$

In this formula  $p_1$  and  $p_2$  are the disease prevalences in the treatment and control communities, respectively,  $k$  is the coefficient of variation of disease prevalence between communities,  $f$  is the number of individuals per community and  $n$  is the number of communities. The Z's in the formula represent standard normal quantiles for appropriate type I and type II error rates. Disease prevalence in the control communities and the coefficient of variation are based on the baseline survey data.

Although the investigators cannot be formally blinded to the treatment assignments, only pooled results (over the two study arms) will be presented by the statistician at investigator meetings.

[figure not shown]
**Table 2. Power for comparing treatment ( $n = 10$ ) and control communities ( $n = 10$ ) given number per community, prevalence,  $\alpha = 0.05$  (1-tailed), coefficient of variation = .10 and indicated reduction in disease in treatment cities. Number of GPS results is reduced from 600 to 500 to allow for refusal to provide biologic samples.**

	Number per community			Percent reduction		
	General	FSW	Prev	30	40	50
	population			Percent	Percent	Percent
Any STD	500		.10	.99	.99	.99
		200	.14	.87	.98	.99
Chlamydia	500		.04	.86	.98	.99
Trichomonas	250		.05	.72	.92	.99
Syphilis	500		.01	.41	.63	.81
HIV	500		.005	.27	.40	.57

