#### **FSW Survey**

For this study, FSW were defined as women who offer their personal sex services at venues of sex work identified in the participating cities. The goal for each survey included 200 FSW enrolled in each of the cities (24 cities at baseline and 20 cities in outcome surveys), for a total of 4,800 at baseline and 4,000 in 2005 and in 2006. Enrollment was carried out in the same cities selected for the GPS conducted during 2002-03 for the baseline survey and 2005 and 2006 surveys, and according to the same timeline and timeframe as the GPS in the 2005 and 2006 surveys (3 months).

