## **FSW Survey**

Local teams began field activities by performing a census of sex work venues (places where FSW meet their potential clients, e.g. brothels, bars or streets). The health promoter and key informants within each city identified these venues. Team members recorded the location and characteristics of the venues, as well as the approximate number of FSW expected to be found at the venue at different times during an average week. The census ended when all accessible sex work venues were recorded. Although it was expected that not all sex work venues would be identified by the census, extremely hard-to-reach venues were considered to be likely of relatively low epidemiological importance, as they tended to serve small closed circles of clients. At the end of the census, copies of the field work records were sent to the UPCH in Lima. In cities with more than 200 FSW identified by the census, a sample of about 200 women were selected by the time-location sampling method. In cities where fewer than 200 FSW were identified, the local team attempted to enroll all FSW identified.

Local teams visited commercial sex venues and invited all FSW present in that venue to participate in the study, and completed interviews and sample collection for this study in a single visit for all participants. After providing verbal informed consent, study participants completed an interviewer-administered questionnaire and underwent HIV and STD counseling and testing. All participants received a copy of the informed consent. Basic demographic data were collected from any FSW present at the venue during the visit but who do not meet the eligibility criteria or who refuse to participate.

Field work teams for each city included three counselors, a laboratory technician and a health promoter, usually a peer FSW. All counselors attended a centralized training workshop before the beginning of field activities. In addition to training in selection of study participants and the appropriate completion of the study questionnaire, the workshop included modules on

ethical issues including appropriate consent procedures granting confidentiality and avoiding any form of coercion. Laboratory technicians received training on appropriate techniques for sample collection, processing, and shipping, as well as on biosafety.

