### 1.2 FSW & Client Surveys in 2003: Sampling, Participation and Responses

Prostitution is legal in Peru and is regulated by the national government and local authorities. Traditionally, the MINSA (Ministry of Health) anti-venereal disease clinics have offered periodic checkups to FSWs. Starting in 1996, the MINSA established a nationwide system for improved voluntary periodic clinical examination and treatment directed to FSWs, setting up STD reference centers in all the main cities of Peru. The system also included the use of peer educators visiting sex work venues to promote safer behaviors and the use of the clinical services offered by the government. In 1998 the MINSA started a sentinel surveillance system directed to high risk populations, including FSWs. Nationwide surveys of FSWs have been carried out in years 1998, 2000, and 2001. These surveys included mostly FSWs using the services of the STD reference centers. A 2003 survey was conducted in collaboration with the PREVEN study, and was carried out at sex work venues. The sampling method and study procedures are described in greater detail in Sections 3.2 and 4.2, respectively.

During January-March 2003, [name] (a co-investigator for this project), the OGE (Peruvian General Office of Epidemiology), and the regional AIDS and STD Offices undertook surveys of FSW and their clients in the same 24 cities. Our 2003 time-venue baseline survey of FSW and clients achieved 87.1% (range 63% - 100% per city) participation from FSW and 82.8% participation from clients. Of 4494 FSW participants, nearly all responded to sensitive questions, 98.8% provided blood samples, and 97.4% provided vaginal swabs. Of 4504 client participants, 97.7% provided blood and 95% (those able to void) provided urine.

**STD prevalences for FSW and Clients of FSW:** 14.5% of FSWs had chlamydia, 3.5% had gonorrhoea, 7.9% had trichomonas and 3.9% were RPR reactive. Data suggest that approximately 0.25% of participating FSWs had acquired HIV infection within the last year.

Among clients of FSW, 4.0 % had chlamydia and had 0.2% gonorrhoea. RPR reactivity was found in 5.6% of those with and 2.2% of those without recent history of genital ulcer ( $p < .05$ ). Data suggest that approximately 0.25% of the clients acquired HIV infection within the last year.

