## 6. STATISTICAL CONSIDERATIONS

### 6.1 Review of Study Design

This CRT is designed to test a multi-faceted intervention to reduce STDs. It will be conducted in 20 medium sized (> 50,000 people) cities in Peru. Ten cities will be randomized to the intervention and ten cities will serve as controls. The intervention consists of programs to educate pharmacy workers and health care providers, as well as outreach to FSWs. The primary endpoint will be a positive test for gonorrhea and/or chlamydia and/or trichomoniasis, and/or syphilis in a high risk group of FSW and in the lower risk young adult general population, as measured by the surveys described previously. The secondary endpoints that will be evaluated are positive tests for bacterial vaginosis and HIV. The study has power to determine if the intervention can reduce the burden of these STDs in the general population by 30-50% (depending on the STD). Changes of this magnitude have clear implications for public health. Smaller effects, even if present, may not be sufficient to change public health practice and, in any event, would be logistically very difficult to detect.

The surveys described above will be conducted in the 20 cities mentioned above over a period of 3 months. The proposed household based general population survey of men and women 18 to 29 years of age will be used to evaluate the study endpoints. In addition, we will conduct a venue-based survey of FSWs. Cluster sampling will be used for the former, while time-location sampling will be used for the latter survey.

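### The FSW Any STD row of Table 2 does not follow from its printed inputs, and its prevalence of .14 is below the baseline FSW chlamydia rate alone

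*Supplement*

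**What the plan says.** The Power Calculations section of the 2010 Protocol Summary (Section III) offers "power calculations for testing for a 30-50% reduction in the primary STD outcomes between the treatment and control communities" and takes FSW separately. It adds: "These calculations make use of the standard sample size/power formula for matched community randomized trials, as shown below". The caption of Table 2 fixes alpha at .05 one-tailed, k at .10 and 10 communities per arm. On the source of the inputs it says: "Disease prevalence in the control communities and the coefficient of variation are based on the baseline survey data".

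The FSW row reads: 200 per community, prevalence .14, power .87, .98 and .99 for reductions of 30, 40 and 50%. The same table stands in section 6.2 of the April 2006 Trial Summary.

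Section 1.2 of that Trial Summary reports the baseline FSW survey: "14.5% of FSWs had chlamydia, 3.5% had gonorrhoea, 7.9% had trichomonas and 3.9% were RPR reactive". The Outcomes section of the Protocol Summary defines the FSW secondary endpoint as any of chlamydia, gonorrhoea, trichomonas or syphilis at RPR 1:8 or higher.

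On numbers, the FSW Survey section says "The goal for each survey included 200 FSW enrolled in each of the cities". The sampling section qualifies this: "In cities where fewer than 200 FSW were identified, the local team attempted to enroll all FSW identified".

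**The concern.** Two things in the row do not fit. The printed power is lower than the printed formula gives for the printed inputs. And the printed prevalence, which should describe a composite of four infections, is slightly below the reported rate of one of them.

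This row is the only power statement for the FSW composite, which is listed first among the secondary endpoints. A reader who uses it to judge what the FSW comparison could detect is relying on a figure that cannot be traced to its stated inputs. It was also computed one-tailed, whereas the Introduction and the Primary and Secondary Analysis sections now specify a two-tailed test on 8 degrees of freedom.

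**Working it through.** **Formula.** The printed sample-size formula, solved for power, is

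power = Φ( √[(n − 2)(p1 − p2)² / V] − z), with V = p1(1 − p1)/f + p2(1 − p2)/f + k²(p1² + p2²).

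Inputs from Table 2 and its caption: n = 10, k = .10, z = 1.645. Here p2 is the control prevalence and p1 the prevalence after the stated reduction.

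**Rows that reproduce** (30/40/50% reduction):

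| Row | f | Prevalence | Computed | Printed |
|---|---|---|---|---|
| Any STD, general population | 500 | .10 | .990/1.000/1.000 | .99/.99/.99 |
| Chlamydia | 500 | .04 | .860/.982/.999 | .86/.98/.99 |
| Trichomonas | 250 | .05 | .720/.922/.990 | .72/.92/.99 |
| Syphilis | 500 | .01 | .415/.626/.815 | .41/.63/.81 |
| HIV | 500 | .005 | .266/.404/.566 | .27/.40/.57 |

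All agree within about .01, if the table is taken to print nothing above .99. The formula is therefore being read as its authors used it.

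**FSW row as printed** (f = 200, p2 = .14), 30% reduction, p1 = .098:

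- V = (.0884 + .1204)/200 + .01 × (.0096 + .0196) = .001044 + .000292 = .001336
- √(8 × .042² / .001336) = 3.25
- power = Φ(3.25 − 1.645) = .946, against the printed .87, a gap of 7.6 points

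At 40% the result is .998 against .98, and at 50% it is 1.000 against .99. Only the 30% cell is far off.

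**Which input differed?** Changing one input at a time:

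| Change | 30% | 40% |
|---|---|---|
| Prevalence .10 (f = 200, k = .10) | .874 | .986 |
| f = 135 (prevalence .14, k = .10) | .870 | .985 |
| k = .165 (prevalence .14, f = 200) | .870 | .985 |

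Each comes close to .87/.98, so the arithmetic cannot single one out.

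**The prevalence.** From the rates in Trial Summary section 1.2:

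- Floor (all other infections in women who also have chlamydia): .145
- Chlamydia, gonorrhoea and trichomonas, if independent (an assumption): 1 − .855 × .965 × .921 = .240
- The same three with no overlap: .145 + .035 + .079 = .259
- Ceiling (no overlap, every RPR-reactive woman counted whatever the titre): .259 + .039 = .298

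At k = .10, f = 200 and a 30% reduction, the printed formula gives .951 at .145, .984 at .20 and .998 at .30.

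**The test now planned.** Two-tailed power is taken from the noncentral t on 8 df with δ = √[10(p1 − p2)²/V]. This allows neither for precision gained from the baseline covariate nor for precision lost to baseline imbalance. At prevalence .14, f = 200 and k = .10 it gives .888/.991/1.000.

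For a restated row, assume prevalence .25, and f = 182 from the baseline yield (4494/24 = 187 women per city, times .974 giving swabs). For a 30% reduction p1 = .175, the binomial part of V is (.1444 + .1875)/182 = .001823, and p1² + p2² = .0931:

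| k (assumed beyond .10) | V | δ | Power |
|---|---|---|---|
| .10 | .002755 | 4.52 | .976 |
| .15 | .003919 | 3.79 | .91 |
| .20 | .005549 | 3.18 | .80 |

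**The case against.** **The row is close to right for the test now planned.** Two-tailed power on 8 df at .14 is .888, within 2 points of the printed .87. That is so, but it is not the formula or sidedness the table states, and the same method gives .761 for the chlamydia row against the printed .86. It does not explain the row.

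**The error is conservative and concerns a secondary endpoint.** This stands, at k = .10. No sample size, test or conclusion in the plan depends on the cell.

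**The gap between .14 and 14.5% is small, and 14.5% covers all 24 surveyed cities, not the control cities.** Also true. The documents give no control-city FSW rate, and the larger gap is to the four-infection composite. The gonorrhoea and trichomonas rates are themselves uncertain. The Laboratory Methods section reports that 48% of clinician-collected AMPLICOR gonorrhoea positives were APTIMA positive, and that InPouch culture had roughly 50% sensitivity. The firm statement is therefore a composite of at least .145; the higher figures rest on the reported rates and on assumed overlap.

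**The 182 per city comes from baseline.** It averages 24 cities, of which 20 entered the trial. At prevalence .25 and k = .10 it moves two-tailed power only from .982 (f = 200) to .976, so it is a minor part of the point.

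A reader might infer that the row was computed at prevalence .10, the value in the row above. That fits, but not exactly: the 40% cell would be .986, which rounds to .99, and a different f or k fits as well.

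**Conclusion.** The FSW row is inconsistent with its own inputs. The formula gives .946 where .87 is printed for a 30% reduction, and the method is confirmed by the five rows that do reproduce. Separately, .14 cannot be the composite prevalence in the baseline survey that the section names as its source. Both results follow from the documents' figures; only the values inside the .145 to .30 range need an assumption about overlap.

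Two stronger conclusions are not supported. One is that a null FSW result would be dismissed as underpowered: a stated power of .87, and .98 for a 40% reduction, would not lead a reader there. The other is that the FSW comparison demonstrably had very high power. That depends on k = .10. The documents give no FSW-specific between-city variation, and k is one of the inputs that may have differed in this row. At an assumed k of .20 power for a 30% reduction is about .80.

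Severity: a minor correction to a stated power figure for a secondary endpoint.

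**What to change.** Restate the FSW row of Table 2 with:

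- the observed baseline prevalence of the FSW composite as the plan defines it, under the final assay rules;
- the between-city k estimated from the FSW survey, with the value printed in the row if it differs from the caption's .10;
- the expected number of women per city with complete results, in place of the goal of 200.

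Recompute power for the two-tailed 8-df test and show it over a range of k, since k matters most at this prevalence. If the printed figures came from a different f or k, say so in a footnote.

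The cost is one table row and a note, from baseline data the study already holds. Design, sample size and analysis do not change.

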**Table 1. Non-response/No. returning questionnaire**

	Male (7505)	Female (7801)
Ever had sex	352/7485 (4.7%)	388/7781 (5.0%)
Age at sexual debut (if experienced)	335/6275 (5.3%)	355/5885 (6.0%)
Anal sex with last partner (if experienced)	622/6276 (9.9%)	498/5885 (8.5%)

**STD prevalences for young adults in the general population:** Among men ages 18-29, 4.0% had chlamydia and 0.3% had gonorrhea; 0.4% tested positive for HIV, which was significantly associated with a high number of lifetime partners ( $p < 0.001$ ), recognizing at least one of the last three partners as casual ( $p < 0.001$ ), reporting sex with another man in the last year ( $p < 0.001$ ) and reporting unprotected sex with a FSW in the last year ( $p < 0.01$ ). Among women ages 18-29, 6.8% had chlamydia, 0.8% had gonorrhea, 5.2% had trichomonas and 0.1% tested positive for HIV.

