- 6) Rate of Incomplete Testing. The DSMB noted that the proportion of participants with incomplete laboratory data was higher in the control arm than the intervention arm. The study team was advised to investigate possible reasons for imbalance, which could potentially lead to selection bias, and to consider ways of minimizing this during the final follow-up.
- 7) Trichomoniasis. The DSMB reported their concerns about the validity of the TV data due to outlying values in some cities, very low correlation between baseline and follow-up TV rates, a low matching correlation, and the lack of standardization in this endpoint noted by the study team. Since TV rates were relatively high compared with other STIs, there was concern that *noise* in this endpoint could unduly influence the trial results. The DSMB therefore recommended that the primary endpoint for the trial should be amended by omitting TV from the composite STI variable. Sample size calculations should be rechecked to confirm that the trial is still adequately powered for the amended endpoint, although this is expected to be the case. Despite this recommendation, the DSMB considered that intervention effects on TV were also of intrinsic interest. The study team should investigate whether TV testing could be repeated or confirmed in a central location, using standardized procedures. If so, separate analysis of TV findings could be carried out in addition to analysis of the primary endpoint.
- 8) Matched Analysis. Based on information given in the closed report and the strong matching correlation achieved for the amended primary endpoint, the DSMB recommended that the matched pairs should be retained in the final data analysis.

- 9) Chlamydia. Noting that some women provided urine while some provided vaginal swabs for CT testing, the DSMB recommended that the combined prevalence (based on *either urine or vaginal swab*) be used in the primary analysis. A secondary analysis (in women) should be performed based on vaginal swabs alone, providing take-up rates of swabs were similar in the two treatment arms.

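### Table 2's printed powers do not match the baseline prevalences cited for chlamydia and HIV, nor the two-tailed test on 8 degrees of freedom that the plan specifies

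*Supplement*

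**What the plan says.** The Power Calculations section of the 2010 protocol summary presents "power calculations for testing for a 30-50% reduction in the primary STD outcomes between the treatment and control communities". It gives a matched-community formula and states the source of the inputs: "Disease prevalence in the control communities and the coefficient of variation are based on the baseline survey data". The caption of Table 2 fixes alpha at 0.05 "1-tailed), coefficient of variation = .10 and indicated reduction in disease in treatment cities", and adds: "Number of GPS results is reduced from 600 to 500 to allow for refusal to provide biologic samples". Those 600 are 300 men and 300 women per city. The chlamydia row uses 500 per city and prevalence .04, with powers .86, .98 and .99. The HIV row uses 500 and .005, with powers .27, .40 and .57.

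The baseline figures are in section 1.1 of the April 2006 trial summary. For men: "Among men ages 18-29, 4.0% had chlamydia", and 0.4% had HIV. For women: "6.8% had chlamydia, 0.8% had gonorrhea, 5.2% had trichomonas", and 0.1% had HIV.

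The Primary Analysis section of the 2010 summary, and the latest Data Analysis Plan under Inferential analyses, specify a regression on ten pair differences. The test is two-tailed at 0.05 with 8 degrees of freedom. The same analysis serves the individual infections. The introduction to the summary says that two-tailed tests were adopted for all analyses after the DSMB review. A footnote dates the power calculation to March 2006, before that change.

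**The concern.** Table 2 is the only statement in the current protocol of what the trial can detect, and a null result will be read against it. Two things do not fit.

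- **Inputs.** A sample of 500 that is half women cannot have 4.0% chlamydia if men have 4.0% and women 6.8%. The HIV value of .005 lies above both sexes' baseline figures, so no mix of the two yields it. The trichomonas row, by contrast, pairs 250 women with .05, close to the women's 5.2%.
- **Test.** The table's powers are for a one-tailed normal test. The analysis to be run is two-tailed and refers to a t distribution on 8 df, which is more demanding.

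The two faults push chlamydia in opposite directions. For HIV both lower the power, and for the remaining rows the change of test does.

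**Working it through.** **Inputs.** Ten cities per arm (section 6.1 of the trial summary: "Ten cities will be randomized to the intervention and ten cities will serve as controls"), so n = 10 pairs; f = 500, or 250 for trichomonas; k = .10; prevalences as printed.

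**Formula.** Solving the protocol's formula for power, with p1 the control prevalence and p2 = 0.7 p1 for a 30% reduction (the expression is symmetric in the two arms):

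V = p1(1−p1)/f + p2(1−p2)/f + k²(p1² + p2²)

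Power (one-tailed) = Φ( √[(n−2)(p1−p2)²/V] − 1.645 )

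**Reproducing the plan's chlamydia figure.** p1 = .04, p2 = .028:

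- V = .0000768 + .0000544 + .0000238 = .0001551
- √(8 × .012² / .0001551) = 2.726
- Φ(2.726 − 1.645) = .86, as printed.

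At 30% the other general-population rows also reproduce: composite .990, trichomonas .720, syphilis .415 and HIV .266, against .99, .72, .41 and .27. The FSW row does not: .14 with f = 200 gives .95 against .87 printed.

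**Both-sex baseline prevalences at a 1:1 mix.**

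- Chlamydia: (4.0% + 6.8%)/2 = 5.4%. Weighting by the 7,505 men and 7,801 women in Table 1 of the trial summary also gives .054.
- HIV: (0.4% + 0.1%)/2 = 0.25%.

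**One-tailed, corrected prevalence.**

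- Chlamydia, p1 = .054, p2 = .0378: V = .0002184; √(8 × .0162² / .0002184) = 3.101; Φ(1.456) = .93. The 40% and 50% cells become .996 and >.999, within two points of those printed.
- HIV, p1 = .0025, p2 = .00175: V = .00000857; √(8 × .00075² / .00000857) = .724; Φ(−.920) = .18. The 40% and 50% cells become .26 and .36, against .40 and .57.

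**Planned test.** Noncentral t on 8 df, critical value 2.306, noncentrality √[n(p1−p2)²/V] with n = 10. The n−2 in the normal formula is itself a small-sample allowance, so I do not apply it again with the t. The last column shows the result if it is kept.

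| Row (30%, k = .10) | Printed | Noncentrality | Two-tailed, 8 df | Same, n−2 kept |
|---|---|---|---|---|
| Chlamydia at .04 | .86 | 3.047 | .76 | .67 |
| Chlamydia at .054 | – | 3.467 | .86 | .78 |
| Trichomonas at .05 | .72 | 2.492 | .59 | .50 |
| HIV at .0025 | .27 (at .005) | .810 | .11 | .10 |
| Composite at .10 | .99 | 4.427 | .97 | .93 |

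**Sensitivity to k, composite at 30%, two-tailed on 8 df (n = 10).** .97 at k = .10, .90 at .15, .79 at .20, .66 at .25, .54 at .30. This range is my assumption; the documents report no city-level prevalences and no coefficient of variation.

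**The case against.** **The table is openly dated and labelled one-tailed, and its arithmetic is sound.** True for the general-population rows, which reproduce. What is disputed there is two inputs and the test, not the calculation. But the current protocol carries the table forward as its power statement, beside an analysis that it does not describe.

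**The text speaks of control communities, and the 4.0% and 6.8% come from all 24 baseline cities.** This stands as a caution. Control-city chlamydia is not given, and the DSMB noted that baseline composite prevalence was generally higher in intervention cities. Control cities would need about three-quarters of the overall figure (.04/.054 = .74) to justify .04. That .04 was taken from the men is therefore an inference from the match. The same argument does not readily rescue HIV, where control cities would need twice the overall figure.

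**The chlamydia slip is conservative and concerns a secondary endpoint.** Correct. It does not enter the composite row, and correcting it raises power.

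**A reader might infer that a common k of .10 must be wrong.** The documents do not support that. They give no value to set against it, and a rounded common value may still derive from baseline data. The DSMB's remark on outlying trichomonas values concerned local cultures, since replaced by NAAT for the baseline and 2006 surveys. The DSMB also noted a strong matching correlation for the composite without trichomonas.

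**A reader might also infer that a DSMB instruction was ignored**, since it wrote: "Sample size calculations should be rechecked to confirm that the trial is still adequately powered for the amended endpoint". That request was tied to a composite omitting trichomonas, which the final protocol did not adopt after NAAT retesting. Reprinting the table does not breach it.

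**Conclusion.** The point holds for the chlamydia and HIV prevalences and for the mismatch between the table and the test. At a 30% reduction and k = .10:

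- Chlamydia moves from .86 to .93 on prevalence alone. With the planned test as well it returns to .86, so the printed figure is about right only because the two faults offset.
- HIV is overstated: .18 against .27 on prevalence alone.
- Trichomonas is overstated: .59 against .72 on the test alone.
- The primary composite loses little: .97 against .99. These figures do not show that the trial is underpowered for its primary endpoint.

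Whether composite power is really that high depends on k, which is unreported rather than refuted.

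The figures assume a 1:1 sex mix and 24-city prevalences that hold in the control cities. The two-tailed figures also ignore both effects of the baseline covariate: variance that it removes, and precision lost when the mean baseline difference is not zero. With about 1.25 expected HIV cases per city (500 × .0025), the HIV figures are rough.

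**What to change.** Reprint Table 2 with both-sex baseline prevalences for chlamydia (about .054) and HIV (about .0025), or with the control-city values if those are what was meant, stating which. Compute power for the two-tailed test on 8 df and say how the noncentrality is formed. For each outcome, report the within-pair k estimated from the baseline survey, with binomial variance removed. Where it cannot be estimated, show power over a range such as .10 to .30. Recheck the FSW row at the same time, since its printed .87 does not follow from its inputs.

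The cost is one recalculation from data already held. The sample, the endpoint and the analysis do not change. Some stated powers will become less favourable.
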